Components of the CGA (e.g. comorbidity, functional status, geriatric syndrome, nutritional status) have high prognostic value for predicting morbidity and mortality in older adults.(16-20) In addition, two recent large studies developed models for predicting chemotherapy toxicity in older adults with cancer which includes geriatric variables. In the model developed by the Cancer and Aging Research Group, the geriatric variables that predicted chemotherapy toxicity included: age ≥ 72 years, hearing impairment, history of falls, dependence on medication administration, limitation in mobility and decreased social activity.(21) In another model known as the Chemotherapy Risk Assessment Scale for High-Age Patients (CRASH) score, the geriatric variables that predicted chemotherapy toxicity in patients aged ≥ 70 years included: dependence in instrumental activities of daily living (IADL), impaired mini-mental status examination (MMSE) score and impaired mini-nutritional assessment score (MNA).(22) Both chemotherapy toxicity prediction models are currently undergoing external validation.

Geriatric assessment can also influence treatment decisions with two published studies demonstrating that geriatric assessment prior to chemotherapy led to modification in chemotherapy regimen in 39-50% of patients.(23, 24) In one study of 161 patients, pre-chemotherapy geriatric consultation resulted in 76% of patients undergoing some form of geriatric intervention and 49% of patients having modification of the initially proposed chemotherapy regimen – these modifications consisted of higher intensity therapy in 28%, lower intensity therapy in 18% and delayed therapy in 3%.(23)

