3.7. Study endpoints

3.7.1. Summary of Endpoints

The primary and secondary endpoints are summarised in the table below. The primary endpoint of this study is health-related quality of life (HRQoL). The secondary endpoints are survival, function, mood, nutrition, chemotherapy delivery and healthcare and aged care service utilisation.

Primary Endpoint	Measures
Trial Outcome Index	
The Trial Outcome Index (TOI) consists of the linear transformation from 0-100 of the unweighted summed score of the physical functioning (PF2), role functioning (RF2) and social functioning (SF) scales of EORTC QLQ-C30, with the mobility (MO) scale of the QLQ-ELD14.
 $TOI = PF2 [QLQ-C30] + RF2 [QLQ-C30] + SF [QLQ-C30] + MO [QLQ-ELD14]$ 
The individual scales on the QLQ-C30, QLQ-ELD14 and EQ-5D-5L will be reported in the secondary and tertiary HRQoL analyses to assist in interpretation of the primary endpoint.

Secondary Endpoints	Measures
Function	
 • ECOG performance status (self-reported) • Karnofsky performance status (self-reported) • Katz ADL scale • OARS IADL scale

Survival	
 • Overall survival
Mood	
 • PHQ -9 • GAD-7
Nutrition	
 • Self-MNA
Health Utilities	
 • EQ-5D-5L
Chemotherapy delivery	
 • Initial dose (standard or reduced dose; dose adjustments due to CGA) • Subsequent dose (dose delay or dose reduction, discontinuation of chemotherapy due to toxicity)
Healthcare utilisation	
 • Hospitalisation (number, type, length of hospital stay, reason) • Emergency department visits (number, reason) • Referrals (type, date referred, date seen) • Medical consultations • Type of Pharmaceutical Benefit Scheme (PBS)-listed medications
Institutionalisation	
 • Social situation • Level of care

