2.6. Endpoints

2.6.1. Summary of Endpoints

The primary and secondary endpoints are summarised in the table below. The primary endpoint of this study is health-related quality of life (HRQOL). The secondary endpoints are survival, function, mood, nutrition, chemotherapy delivery, healthcare utilisation and institutionalisation.

Primary Endpoint	Measures
ELderly Functional Index (ELFI)	
The ELderly Functional Index (ELFI) consists of the linear transformation from 0-100 of the unweighted summed score of 12 items from the QLQ-C30 and QLQ-ELD14, covering: physical functioning (PF2; QLQ-C30 items 1-5), role functioning (RF2; QLQ-C30 items 6-7), social functioning (SF; QLQ-C30 items 26 and 27) and mobility (MO; QLQ-ELD14 items 31, 33 and 34).
 
The individual scales on the QLQ-C30, QLQ-ELD14 and EQ-5D-5L will be reported in the secondary and tertiary HRQOL analyses to assist in interpretation of the primary endpoint.

Secondary Endpoints	Measures
Survival	
 Overall survival
Function	
 Self-reported ECOG performance status Self-reported Karnofsky performance status Katz ADL scale OARS IADL scale
Mood	
 PHQ -9 GAD-7
Nutrition	
 Self-MNA
Health Utilities	
 EQ-5D-5L
Chemotherapy delivery	
 Initial dose (standard or reduced dose) Subsequent dose (dose delay or dose reduction, discontinuation of chemotherapy)
Healthcare utilisation	
 Hospitalisation (number, type, length of hospital stay, reason) Emergency department visits (number, reason) Referrals (type, date referred, date seen) including Allied Health and Oncology Rehabilitation Program Medical consultations Type of Pharmaceutical Benefit Scheme (PBS)-listed medications
Institutionalisation	
 Social situation Level of care

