3.1. Overview

All analyses will be conducted as defined in a formal statistical analysis plan (SAP) for the analysis and presentation of data. The SAP will be finalised prior to commencement of study analysis and approved by the Trial Management Committee (TMC).

This document constitutes the formal statistical analysis plan (SAP).

All analyses will be conducted according to the intention-to-treat (ITT) principle: all eligible and evaluable participants will be included in the analysis and analysed according to the arm randomised to (using the as-randomised participant population). By using the ITT principle, the benefits of randomisation are maintained (i.e. that the trial arms are similar except for intervention).

Baseline characteristics by treatment arm will be summarised in frequency tables and by use of descriptive statistics for quantitative variables. Univariate associations will be identified using independent T-test for comparing means, χ^2 or Fisher's exact test for comparing categorical data. Confounder bias will be minimised with logistic regression by adjusting for age plus other relevant differences between the groups (comorbidity, metastatic disease, chemotherapy dose reduction at the outset) in bivariate and multivariate analysis.

Summary tables will be prepared giving numbers of participants by treatment arm and by randomisation irregularities, treatment compliance, eligibility infringements, and losses to follow-up (as per CONSORT guidelines).(19)

Table 1. Baseline characteristics by treatment group

Characteristic	Intervention	Usual Care
Age		
Mean		
Median		
Range		
Sex		
Male		
Female		
Marital status		
Married		
Separated, divorced		
Widowed		
Single		
Household composition		
Lives in the community with spouse, partner or child		
Lives in the community alone		
Lives in residential care		
Cancer site		
Upper gastrointestinal		
Lower gastrointestinal		
Lung		
Urogenital		
Breast		
DLBCL		
Other, not specified		
Cancer stage		
II		
III		
IV		

Treatment intent		
Curative/neoadjuvant/adjuvant		
Palliative		
Initial anti-cancer treatment		
Cytotoxic chemotherapy		
Immunotherapy		
Targeted therapy		
Treatment line		
1 st line		
2 nd line		
3 rd line and beyond		
Patient-reported outcomes		
ELFI score		
EQ-5D-5L utility score		
ECOG 0-1		
KPS \geq 80		
IADL unimpaired		
ECOG 0-1		
KPS \geq 80		
PHQ-9		
GAD-7		

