- Institutionalisation A secondary endpoint of this study is the hazard ratio of institutionalisation of participants in the two treatment arms; this will be compared between treatment arms. In addition, the level of care level of care and social situation will also be described in the treatment arms.

The following endpoint definition was changed from the protocol:

- Chemotherapy delivery: the proportion of participants with dose delays in the two treatment arms at 12 weeks and 24 weeks. Dose delay is defined as a delay of more than 3 days in the start of chemotherapy measured since the start of the previous cycle.

The following endpoints were not defined in the protocol, but will be analysed as exploratory endpoints to supplement the pre-specified secondary endpoints:

- QLU-C10D health utility
- QLU-C10D health utility score in the two treatment arms at 12 weeks and 24 weeks will be compared between treatment arms.(27, 28)
- The QLU-C10D health utility scores will also be used in the health economic analysis, in place of the EQ-5D-5L scores, to determine if the same or different conclusions would be reached with either utility measure.
- Chemotherapy delivery
- Primary dose reduction (PDR) will be compared within treatment arms. PDR is defined as dose of chemotherapy which is less than the dose recommended for given regimen in current treatment guidelines by NCCN (excluding round-off).
- Mean % dose reduction at outset will be compared within treatment arms.
- Median % dose reduction at outset will be compared within treatment arms.
- Early discontinuation of chemotherapy will be compared within treatment arms.
- Mean cycles of chemotherapy delivered will be compared within treatment arms.
- Median cycles of chemotherapy delivered will be compared within treatment arms.

Table 4. Summary of secondary and additional exploratory endpoints, data type, data timepoints and statistical tests are listed in the table below.

Endpoints	Data Type	Data output	Data Timepoints	Statistical Tests
Function				
ECOG-PS	Categorical ordinal (0,1,2,3,4)	contingency table	Baseline Wk12 Wk24	contingency table analysis
KPS	Categorical ordinal (30,40,50,60,70,80,90,100)	contingency table	Baseline Wk12 Wk24	contingency table analysis
Katz ADL scale	6-item, categorical dichotomous scale (i) → dichotomous outcome (unimpaired, impaired) (ii) → dichotomous outcome (any decrease in ADL)	1. unimpaired vs impaired 2. decrease in ADL	Baseline Wk12 Wk24	contingency table analysis

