OARS IADL	7-item, 3-point Likert scale (i) → categorical dichotomous (unimpaired, impaired) (ii) → categorical dichotomous (any decrease in IADL)	1. unimpaired vs impaired 2. decrease in IADL	Baseline Wk12 Wk24	contingency table analysis
Mood				
PHQ9 (depression)	9-item, 4-point Likert scale → categorical ordinal (none, mild, moderate, severe) → categorical dichotomous (not depressed, depressed)	contingency table	Baseline Wk12 Wk24	contingency table analysis
GAD7 (anxiety)	9-item, 4-point Likert scale → categorical ordinal (none, mild, moderate, severe) → categorical dichotomous (not anxious, anxious)	contingency table	Baseline Wk12 Wk24	contingency table analysis
Nutrition				
Self-MNA	6-item questionnaire → categorical dichotomous (malnourished/at risk vs normal) → categorical ordinal (malnourished, at-risk, normal)	1. malnourished/at risk vs normal 2. malnourished vs at-risk vs normal 3. decrease in self-MNA	Baseline Wk12 Wk24	contingency table analysis
Health Utilities				
EQ-5D-5L	5-item, 5-point Likert scale, weighted with Australian utility weights	mean utility weight	Baseline Wk12 Wk18 Wk24	t-test (parametric); or Mann-Whitney test (non-parametric)
QLU-C10D	10-dimensions derived from 13 items of the QLQ-C30, each dimension weighted with Australian utility weights	mean utility weight	Baseline Wk12 Wk18 Wk24	t-test (parametric); or Mann-Whitney test (non-parametric)
Chemotherapy Delivery				
Initial dose (i.e. primary dose reduction)	Categorical dichotomous (full dose, reduced dose)	full dose vs reduced dose	Baseline	contingency table analysis
Mean % dose reduction at outset where applicable	Numerical	mean	Baseline	t-test (parametric); or Mann-Whitney test (non-parametric)
Median % dose reduction at outset where applicable	Numerical	median	Baseline	Mann-Whitney test (non-parametric)
Subsequent dose reduction ≥10%	Categorical dichotomous (yes, no)	yes vs no		contingency table analysis
Subsequent dose escalation	Categorical dichotomous (yes, no)	yes vs no		contingency table analysis
Dose delay >3 days	Categorical dichotomous (yes, no)	yes vs no		contingency table analysis

Early discontinuation	Categorical dichotomous (yes, no)	yes vs no		contingency table analysis
Mean Relative Dose Intensity (RDI)	Numerical	mean		t-test (parametric); or Mann-Whitney test (non-parametric)
Mean cycles delivered	Numerical	mean		t-test (parametric); or Mann-Whitney test (non-parametric)
Median cycles delivered	Numerical	Median		Mann-Whitney test (non-parametric)

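### SAP 3.1 adjusts for initial chemotherapy dose reduction, a post-allocation variable that the intervention can change and that is itself an endpoint

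*Combined protocol and SAP*

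**What the plan says.** SAP 3.1 (Overview) first commits to intention to treat, on the ground that it preserves the comparability created by randomisation. The next paragraph says "Confounder bias will be minimised with logistic regression", and then gives the covariates: "adjusting for age plus other relevant differences between the groups (comorbidity, metastatic disease, chemotherapy dose reduction at the outset) in bivariate and multivariate analysis". It does not say which outcomes the regression is for.

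Initial dose appears elsewhere as a result of treatment, not as a patient characteristic:

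- Protocol 3.7.1 lists it under chemotherapy delivery, a secondary endpoint: "Initial dose (standard or reduced dose; dose adjustments due to CGA".
- SAP 2.6.1 keeps it as a secondary endpoint: "Initial dose (standard or reduced dose".
- SAP 3.5.2 adds an exploratory version: "Primary dose reduction (PDR) will be compared within treatment arms".
- SAP Table 4 gives it a row, "Initial dose (i.e. primary dose reduction", with a contingency-table test and the timepoint Baseline.

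The primary model in SAP 3.4.3 is a linear mixed model for ELFI. Its covariates are baseline ELFI and, optionally, further unnamed baseline variables that predict the outcome.

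**The concern.** In a randomised comparison, a variable that arises after allocation cannot confound the effect of the arm. If the arm influences it, adjusting does harm in one of two ways. Where dose affects the outcome, adjustment blocks that route and removes part of the benefit. Where frailty drives both dose and outcome, comparing arms among patients with the same initial dose compares groups that differ in frailty, so a difference can appear where there is none.

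The route through dose is one that the trial intends. Protocol 1.2.1 expects geriatric care to help partly through its influence on cancer treatment decisions. Protocol 1.1.3 cites two studies in which "geriatric assessment prior to chemotherapy led to modification in chemotherapy regimen in 39-50% of patients". The same quantity cannot serve both as a consequence of the intervention and as a confounder of its effect.

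**Working it through.** **Step 1: where initial dose falls in time.**

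| Event | Place | Timing |
|---|---|---|
| Chemotherapy planned, none in the previous 3 months | SAP 2.2.1, 2.2.2 | At entry |
| Baseline assessment | Protocol 3.6.5.2 | Before allocation |
| Allocation | Protocol 3.6.5.2 | After baseline assessment |
| Geriatric assessment; plan may cover toxicity risk and is reported to the oncologist | SAP 2.4.1 | Within 3 weeks of randomisation |
| Chemotherapy data recorded | Protocol 3.6.1; SAP 2.5.1 | Weeks 12 and 24 only |

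Baseline Table 1 in SAP 3.1 lists type and line of treatment but not dose. Only Table 4 places initial dose at baseline.

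**Step 2: the plan's own figure.** A two-sided t-test at 0.05 with 80% power and effect size 0.5 needs 63.8 per group, so 64 as stated (power 80.1%). That calculation has no covariates, so dropping one leaves it unchanged.

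**Step 3: a mediated effect removed.** All inputs from here on are assumptions. Let the log-odds of a bad binary outcome be −0.6 at full dose, let a reduced initial dose halve the odds, and let the arm have no direct effect. Let reductions rise from 30% (control) to 50% (intervention).

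- Risk at full dose: 1/(1+e^0.6) = 0.3543. Risk at reduced dose: log-odds −0.6 + ln 0.5 = −1.293, giving 0.2153.
- Control: 0.70 × 0.3543 + 0.30 × 0.2153 = 0.3126.
- Intervention: 0.50 × 0.3543 + 0.50 × 0.2153 = 0.2848.
- Total-effect odds ratio: (0.2848/0.7152)/(0.3126/0.6874) = 0.3982/0.4548 = 0.876.
- Within each dose stratum the arms have the same risk, so the adjusted odds ratio is 1.00. The whole effect is gone.

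Adding a direct odds ratio of 0.70 gives intervention risks of 0.2775 and 0.1611, mean 0.2193, odds 0.2809. The total odds ratio is 0.2809/0.4548 = 0.618; the adjusted one is 0.70.

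**Step 4: a spurious effect created.** Now let dose have no effect on outcome, and let an unmeasured frailty score raise the log-odds of both dose reduction and bad outcome by 1 per SD. Reductions again go from 30% to 50%. Dose-reduced patients in the intervention arm are then on average less frail than those in the control arm, and so are the full-dose patients. With 2,000,000 simulated patients the unadjusted odds ratio is 1.00 and the adjusted one 0.865.

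**Step 5: the range.**

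| Assumed scenario | Unadjusted OR | Adjusted for initial dose |
|---|---|---|
| Reductions 30% to 50%, mediation only | 0.876 | 1.00 |
| Same, plus direct OR 0.70 | 0.618 | 0.70 |
| 30% to 50%, frailty only | 1.00 | 0.865 |
| 30% to 50%, mediation and frailty | 0.888 | 0.867 |
| 50% to 30%, mediation and frailty | 1.125 | 1.152 |
| 30% in both arms | 1.00 | 1.00 |

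The first two rows follow from Step 3 (simulation gave 0.872 and 0.618 unadjusted); the others are simulated. Non-collapsibility of the odds ratio does not explain rows one and three, because one of each pair is exactly null. The last row shows the condition: no effect of arm on initial dose, no bias.

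**The case against.** The strongest reply concerns reach. A reader might infer that the primary ELFI result is biased. The documents do not say so. The sentence specifies logistic regression, ELFI is continuous, and SAP 3.4.3 does not name dose reduction. The other ELFI tests in SAP 3.4.4 and 3.4.5 and the tests in Table 4 name no covariates. This stands as far as it goes. What remains open is that 3.4.3 admits unnamed baseline variables while Table 4 labels initial dose Baseline.

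For the same reason, an error rate for the primary test would be unsupported. Suppose reductions rise from 20% to 50% and frailty is worth 0.5 SD of ELFI per SD. The spurious effect is then +0.07 SD if frailty acts on dose at 0.5 log-odds per SD, and +0.13 SD at 1. Including baseline ELFI, which the primary model does, cuts +0.13 to between +0.10 and +0.03 for assumed correlations with frailty of 0.5 to 0.9. The answer depends on the inputs chosen.

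Nor can a rise in dose reductions be assumed. In the one cited study that gives a breakdown (Protocol 1.1.3), regimens moved to higher intensity in 28% and to lower in 18%. Some first doses also cannot respond to the assessment: Protocol 3.6.5.3 allows chemotherapy to start before day 8, while the assessment may come up to 3 weeks after randomisation. No section states when the dose is decided. These points limit the size of the bias and leave its direction open. They do not make the variable a baseline one, since the protocol itself counts adjustments caused by the assessment within the initial-dose endpoint.

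A reader might also infer that the other covariates are picked by significance tests, because the preceding sentence says "Univariate associations will be identified using independent T-test for comparing means". The text is ambiguous: age, comorbidity and metastatic disease are named in advance, and no rule ties them to those tests. Comorbidity and metastatic disease precede allocation and are legitimate covariates.

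**Conclusion.** SAP 3.1 is wrong as written on this one term. It directs adjustment for a variable that follows allocation, that the intervention can change, and that is an endpoint; no other section cancels the instruction. Any adjusted comparison that follows it departs from the total effect, to the extent that the arm changes initial dose, and so conflicts with the intention-to-treat commitment in the same section.

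The conclusion about the covariate rests on the documents alone. The size does not: the odds ratios above are illustrations under assumed rates and effects, and the shift can go either way, so the adjustment cannot be defended as conservative. The finding applies most directly to binary outcomes, such as functional decline, mood and nutrition categories, and possibly 10-unit ELFI deterioration. It extends to the primary mixed model only if initial dose were admitted there as a baseline variable.

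**What to change.** 1. In SAP 3.1, delete dose reduction at the outset from the adjustment set, and name the outcomes for which adjusted logistic models will be fitted.
2. Add a rule for every adjusted analysis, including the optional covariates in SAP 3.4.3. For example: *Covariates are restricted to pre-specified variables fixed before allocation: the baseline value of the outcome, the minimisation factors (treatment intent, tumour type, age, gender, physician-rated ECOG), comorbidity and metastatic disease. No variable determined after allocation is used as a covariate.*
3. Analyse outset dose reduction only as an endpoint, or in a mediation analysis labelled as such and kept apart from the intention-to-treat results.
4. In Table 4, replace the Baseline timepoint for initial dose with one that shows it is observed after allocation.

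The cost is SAP wording. Sample size, data collection and the primary model's structure do not change. It should be done before analysis begins, because a later change of covariates could look driven by results.

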3.2. Sample size

3.2.1. Sample size required

Based on reviews of published studies, a minimal important difference in patient-reported outcome scores has commonly been set at approximately half the standard deviation; that is, equivalent to an effect size of 0.50.(20, 21) An effect size of 0.5 is commonly regarded as a medium difference and a meta-analysis has shown it to be clinically relevant in studies of quality of life using QLQ-C30 as an outcome measure.(22, 23)

The target sample for this study was based on an independent t-test at a 2-sided significance level of 0.05 to have an 80% power to detect a significant between-group difference in ELFI from baseline to 12 weeks with an effect size of 0.5. Under these assumptions, the minimum sample size is 64 evaluable participants in each group (or a total of approximately 128 evaluable participants) who have completed the primary outcome measure at two separate timepoints.

3.3. Baseline Characteristics

3.4. Primary Efficacy Analysis: HRQOL

3.4.1. Overview

The primary efficacy analysis will address the primary objective of this study which is to assess the effects of integrated geriatric care on HRQOL in older adults with cancer receiving chemotherapy. This will involve a hierarchical set of HRQOL analyses, described below as the primary, secondary and tertiary HRQOL analyses.

The primary HRQOL analysis will relate to the primary endpoint of the study, the ELFI, which represents the subset of HRQOL domains most likely affected by the study intervention. The primary HRQOL analysis will employ linear mixed models, with pattern-mixture models and/or joint model of longitudinal and survival data as sensitivity analyses. The secondary HRQOL analyses will also relate to the ELFI and compare: i) the proportions of participants who experience change in ELFI by at least the clinically important threshold, using Fisher's test; and ii) time to change in ELFI by at least the clinically important threshold using log-rank test. Finally, the tertiary HRQOL analyses involve analyses of all the scales of the EORTC QLQ-C30, QLQ-ELD14 and EQ-5D-5L using t-test or Wilcoxon test (according to normality of distribution), to complement the primary and secondary HRQOL analyses, to make full use of all HRQOL data collected and to assist in interpretation of the of the primary endpoint.

